Pharmacy staff will follow the randomization procedures as described in the protocol, and document subject allocation. Pharmacy staff must ensure that the randomization code is broken only in accordance with the unblinding procedures described in the study protocol. Randomization documentation will be filed with the essential study documents stored in the pharmacy until study close out.

Subject Compliance with Study Medication/Intervention

We do not anticipate problems with compliance for the following reasons: (i) Patients are hospitalized, will be followed closely by the research staff, and study drug will be ordered and administered by nursing; (ii) Further, the primary outcome is initial response to the loading protocol. As the study drug is to be given on the day of enrollment we would anticipate near 100% compliance for receipt of at least one load of cholecalciferol. Adherence to the protocol will be recorded as an outcome measure of our pilot study.

Concomitant and Prohibited Meds

[figure not shown]
As per the exclusion criteria, children on digoxin therapy will not be permitted to take part in the trial because of potential interactions with cholecalciferol. Vitamin D administration can increase the risk of hypercalcemia if given to patients on thiazide diuretics and calcium. Therefore, patients who are on thiazide diuretics and also receiving regular, ongoing calcium supplementation above the daily recommended intake will not be permitted to take part in this study (except for those patients who are receiving the calcium supplementation for hypocalcemia).

Both Arms

At the discretion of the health care team, study participants in either arm can receive routine or standard of care daily vitamin D administration (400-800 IU/day). With the exception of study drug administration (enteral cholecalciferol or placebo) there will be no other changes to clinical management. Co-interventions will not be protocolized as the study is blinded and any differences should relate to either random chance or effects from the study drug. Additional vitamin D administration and other major co-interventions will be captured on the case report form.

STUDY PROCEDURES/EVALUATIONS

Schematic of Study Design

Identification of patients, Screening, and Randomization

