Eligible patients will be identified in the intensive care units. Patients will be screened on a daily basis (Monday through Friday) by study staff. The ICU staff including physicians, nurses, pharmacists, dieticians, respiratory therapists as well as patient families will be made aware of the study through information sessions, posters, bi-monthly emails and monthly pamphlets providing study updates (see Appendix H for integrated knowledge translation and consumer engagement plan). Once a patient is determined to meet the study eligibility criteria, with the exception of vitamin D status, a member of the patient's circle of care will ask the legal guardian (and patient where appropriate) if study staff can come and speak to them about a research study. Once permission has been obtained through the circle of care, research staff will approach the family about study participation. If informed consent is obtained, blood will be acquired to determine if the patient meets the eligibility criteria of being vitamin D deficient. Study staff will first call the laboratory to determine if sufficient discard blood is available for the patient. If no discard blood is available, the study team will provide a blood sample package to the bedside nurse, and the blood sample will be collected with the patient's next clinically indicated bloodwork or through existing lines. Research staff will determine vitamin D status using the Qualigen® FastPack IP system (results should be available in approximately <2h), or by sending the sample to a certified laboratory for analysis of 25(OH)D levels. If the 25(OH)D is less than 50 nmol/L the patient will be considered fully eligible and will be randomized into the study.

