Blood measurements will be performed on samples collected during screening and on days 1, 2, 3, 7, and at hospital discharge. If discard blood is used for screening, a separate enrolment sample will be collected from randomized patients to have sufficient quantity for analysis of vitamin D metabolites. If a fresh sample is collected at screening, then a separate enrolment sample will not be required. If routine blood work is not planned for these specific days, and arterial or central venous line access is not available, research blood samples will be collected at the time of the next clinically indicated venipuncture. Urine samples will be collected at enrolment and on Day 3, 7 and at discharge. The amount of urine that will be collected during each sample is approximately 5mL. In order to comply with the CHEO REB guidance for blood sampling, the volume collected for each blood

sample will vary depending on the patient's weight. There are 6 planned blood samples for this study. However, since blood will only be drawn through existing lines or with clinically indicated bloodwork, patients may have less than 6 samples collected. In addition, patients may have additional bloodwork done following specific interventions or triggers. We anticipate that ~15-20% of patients will require an additional sample within the first 30 days for this reason. For low-weight patients, we will evaluate the amount of blood collected to date and if needed, adjust the volume or not collect the trigger sample to remain within the total volume 30 days limit in the CHEO REB guidelines.

Patient Weight	Volume per Sample	Total Volume Collected from Planned Samples
2-3 kg	1.5 mL/sample	9 mL
3-4 kg	2 mL/sample	12 mL
4-5 kg	2.5 mL/sample	15 mL
>5 kg	3 mL/sample	18 mL

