Blood samples at each time point will be analyzed for 25(OH)D levels at study close out. Subsites will store collected samples and they will be shipped to the Coordinating Centre for analysis (see Appendix I for further detail). Ionized calcium will be measured in the research sample collected on Days 3, 7, 30, 60 and 90 unless ionized calcium has been measured through clinical bloodwork in the preceding 24 hours, or a clinical calcium sample is planned for that day. Since blood samples will only be drawn through existing lines or with clinically-indicated bloodwork, we will not consider it a protocol deviation if a research blood sample cannot be collected. Similarly, if a patient cannot produce urine for a urine sample, we will not consider this a protocol deviation. Since we will be timing bloodwork with clinical bloodwork, we have established acceptable time windows for research samples (i.e. if the Day 3 sample is collected on Day 2 or 4, we will consider this acceptable and still include the sample in the analysis).

Research Sample Target	Acceptable Range
Day 0 (Enrolment)	n/a
Day 3	+/- 1 day
Day 7	+/- 2 days
Day 30	+/- 7 days
Day 60	+/- 7 days
Day 90	+/- 7 days

Additional Blood Sampling After Specific Triggers

Clinical interventions: Specific interventions are known to significantly reduce 25(OH)D concentrations, including: cardiopulmonary bypass (CPB), extracorporeal membrane oxygenation (ECMO), plasma exchange^{23,109,110}. Study patients who receive specific interventions after administration of study drug will have their blood concentrations of 25(OH)D determined post intervention. We anticipate that one or more of these interventions will occur in less than 20% enrolled in the study. Similarly, if a patient is consented and the screening 25(OH)D level is >50 nmol/L (patient not eligible), but the patient subsequently undergoes an above-mentioned intervention, a new blood sample (discard whenever possible) will be collected to re-screen the patient. If the 25(OH)D level in the post-intervention screening sample has fallen to <50 nmol/L, the patient will be randomized into the study.

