As there is little experience with weight based enteral vitamin D loading therapy in critically ill children we will plan for interim safety analysis after 15, 30 and 52 patients. After review of the 25(OH)D levels and adverse event data, the Data and Safety Monitoring Committee will be empowered to provide recommendations on stopping the trial or adjusting both the dosing regimen.

Subgroup Analyses

We will evaluate biochemical and clinical outcomes within three different subgroups. First, we will evaluate initial 25(OH)D response in the group of patients under and over 40 kg. Second, we will evaluate and compare changes in biochemistry and clinical measures separately for the groups with starting 25(OH)D above and below 30 nmol/L. Third, we will evaluate and compare 25(OH)D response and clinical measures separately for newborns (age < 30 days) versus older children (age > 30 days).

Feasibility of Recruitment

The planned recruitment rate is up to 67 patients. At CHEO we have between 500 and 600 PICU admissions per year. Of these, we anticipate that up to 50% of patients will either not be eligible, the physician will refuse, or the parents/caregivers will be unavailable or not willing to speak with research staff. Based on both our experience with vitamin D RCTs and previously published work on factors affecting consent in PICU studies in Canada, we anticipate that 50% (n=125, 10/month) of those approached will agree to participate¹¹¹. Of those that choose to participate we anticipate that approximately 50% (n=67, ~5 per month) will be eligible for randomization based on a 25(OH)D under 50 nmol/L. Recruitment rates are difficult to predict, and are frequently slower than expected. Consequently, we will allow up to 2 years for recruitment into this dose evaluation study. The recruitment rate will be enhanced with expansion of the study to the international sites and to the

NICU at CHEO. Recruitment through CVS, and alternate consent procedures for measuring vitamin D during screening will also improve recruitment rate (see Appendix K and Appendix L for Gantt timeline of this study and of the overall research program).

Loss of Follow-Up

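### For children screened on discard blood, nothing places the enrolment sample before the dose, so the secondary baseline can be post-dose in the vitamin D arm

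*Combined protocol and SAP*

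**What the plan says.** Under Identification of patients, Screening, and Randomization, discard blood is the first choice: "Study staff will first call the laboratory to determine if sufficient discard blood is available for the patient". A fresh sample is taken only if none is available.

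Under Blood and Urine Sampling, a fresh screening sample doubles as the enrolment sample. After discard screening, "a separate enrolment sample will be collected from randomized patients to have sufficient quantity for analysis of vitamin D metabolites". In general "blood will only be drawn through existing lines or with clinically indicated bloodwork". If neither routine bloodwork nor an arterial or central line is available, "research blood samples will be collected at the time of the next clinically indicated venipuncture". The table of acceptable ranges in the same section gives n/a for Day 0.

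Under Randomization and Allocation Concealment, the sequence runs from study ID to dispensing to bedside administration. Subject Compliance with Study Medication/Intervention states that "the study drug is to be given on the day of enrollment".

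Under Subgroup Analyses, changes in biochemistry and clinical measures are compared "separately for the groups with starting 25(OH)D above and below 30 nmol/L". Study Endpoints lists vitamin D axis function and change in immune function. I found no section that says which sample supplies the starting value or requires it to precede the dose.

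**The concern.** A fresh screening sample necessarily precedes randomisation, and so the dose. Discard screening loses that ordering, because the enrolment sample comes from children already randomised and must wait for a line or a clinical draw, while nothing makes the dose wait.

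A sample drawn after the dose already carries part of the response in children given cholecalciferol and none of it in children given placebo. Randomisation and blinding do not remove such an error, because it arises after allocation and differs by arm. It would shrink the measured change in the treated arm. It could also move treated children from below to above 30 nmol/L while leaving comparable placebo children where they were, so the arms within each subgroup would no longer be comparable. The Analyses section ties the 30 and 50 nmol/L thresholds to the feasibility of the phase III trial, so this subgroup will be read with interest.

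**Working it through.** **The plan's own figures.** Sample Size assumes a mean baseline of 40 nmol/L, a rise of 70 and an SD of 35. The share below 75 is Φ((75 − 110)/35) = Φ(−1) = 15.9%, against the stated 16%. For power, P(X ≥ 24 | n = 36, p = 0.75) = 90.8%, against the stated figure of about 90%. Both reproduce, and neither uses a measured enrolment sample.

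**Order of events after discard screening.**
1. The screening 25(OH)D is known before randomisation.
2. The child is randomised.
3. The drug is dispensed and given on the day of enrolment.
4. The enrolment sample is taken at some point after step 2. Its place relative to step 3 is not stated.

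**Size if the sample follows the dose.** The inputs are a rise of 70 nmol/L (Sample Size) and its time course. The text on loading-dose trials says levels can be raised within 48–72 hours. Appendix E, the source cited for the predicted level, reports levels one week after dosing. No section says that the full 70 is reached by 72 hours, so I use all three time spans. Linearity is an assumption.

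Bias = 70 × h / T, for a sample h hours after the dose and a rise completed in T hours (nmol/L):

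| h | T = 168 h | T = 72 h | T = 48 h |
|---|---|---|---|
| 2 | 0.8 | 1.9 | 2.9 |
| 6 | 2.5 | 5.8 | 8.8 |
| 12 | 5.0 | 11.7 | 17.5 |

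The apparent rise is 70 minus the bias. At 12 hours it is 65.0 (T = 168) down to 52.5 (T = 48).

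**Effect on the 30 nmol/L split.** This applies if the enrolment value is used as the starting value. A child crosses the cut when the true baseline lies between 30 − bias and 30. At 12 hours that band starts at 25 (T = 168) or 12.5 (T = 48). For illustration, assume true baselines are normal with mean 30 to 40 and SD 10, truncated to 5–50. Among treated children who are truly below 30 and sampled post-dose, the share moved to 30 or above is:

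- bias 2: 16–28%
- bias 6: 46–65%
- bias 12: 78–91%

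**Dilution at arm level.** If 25% of the arm were sampled 12 hours post-dose (illustrative), the mean baseline would shift by 0.25 × 5.0 = 1.25 to 0.25 × 17.5 = 4.4 nmol/L. The documents give neither the true fraction nor the delay.

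**With a pre-dose definition**, the bias is zero in both arms and the plan's sample size and power are unchanged.

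**The case against.** The strongest reply is that a usable pre-dose 25(OH)D already exists for every child. Screening must be resulted before randomisation, and the plan never says that the starting value means the separate enrolment sample. That stands, and it limits the damage to the subgroup. But the plan does not name the screening value either, and it may come from the FastPack device, whereas final reporting of vitamin D status uses mass spectrometry. The screening result also supplies no pre-dose PTH, 1,25(OH)2D, CRP, procalcitonin or cathelicidin.

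Second, waiting for the next venipuncture is a fallback for children with neither planned bloodwork nor a line, and its wording may refer only to the scheduled days. That also stands. A child with a line can be sampled at once, so a reader should not infer that every discard-screened child is affected. The general restriction to lines or clinical bloodwork still covers the enrolment sample.

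Third, blood drawn the morning after an afternoon dose would normally be the Day 1 sample, and the enrolment sample would simply be missing. I accept this. The realistic exposure is a draw later on Day 0.

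Fourth, the Analyses section describes between-group tests with no stated baseline term, so only analyses of change and of the subgroup are exposed. That is correct. The laboratory SOP and procedure manual, which are not among the documents, may also fix the order.

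Finally, one might suspect the enrolment urine as well. The section on hypercalciuria sets it apart from urine evaluated after study drug, which implies that it is pre-dose. It needs only a clarifying word.

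**Conclusion.** The point holds as a gap in sequencing with limited reach. Followed as written, the plan permits a post-dose enrolment sample in discard-screened children, most plausibly those without a line or planned bloodwork, and the resulting error would fall on the vitamin D arm alone. It touches the secondary and exploratory changes in biochemistry and, depending on which value is used, the 30 nmol/L subgroup.

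For an affected child the bias in 25(OH)D is about 2.5 to 9 nmol/L at 6 hours and 5 to 18 nmol/L at 12 hours. This rests on a linear 70 nmol/L rise over one week or over 48 hours respectively. Early kinetics could differ from both. The number of affected children cannot be derived from the documents, and no size can be given for the other markers.

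Two stronger readings are not supported:

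- A reader might infer that every treated child with a baseline of roughly 18 to 30 nmol/L is misclassified. That would require a 12-hour delay, the full rise within 72 hours and no variation between children. Children above 40 kg also receive less than 10,000 IU/kg.
- A reader might infer that the main result is biased. The primary outcome is the treated-arm proportion above 75 nmol/L on day 7. Neither it nor the sample size or stopping rules use the enrolment sample.

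**What to change.** In Blood and Urine Sampling:

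- Replace n/a for Day 0 in the table of acceptable ranges with: before study drug.
- State that baseline is the last sample before study drug, and that a post-dose sample is never used as baseline.
- State that, if no pre-dose enrolment blood was obtained, the screening 25(OH)D is used for the 30 nmol/L subgroup and the other baseline markers are set to missing.
- Clarify that the enrolment urine is collected before study drug.
- Record draw and dose times on the case report form.

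The Analyses section already refers to children who received two doses, so enrolment has begun. For those already enrolled, drug administration is charted. Where draw times are also available, the same rule can be applied before unblinding.

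The cost is a few lines of text and two time fields. No extra blood is needed, and dosing need not be delayed because the rule governs only what counts as baseline. The downside is that a few children will lack baseline PTH, 1,25(OH)2D and inflammatory markers, and a few will have a baseline 25(OH)D from the screening assay rather than from mass spectrometry.

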The Data Safety Monitoring Board (DSMB) will be comprised of two clinical experts and a biostatistician or clinical epidemiologist. Terms of Reference will be created for the DSMB and approved by all DSMB members and the Principal Investigator before recruitment commences. The DSMB will function independently and at arm's length from the Study investigators and the Steering Committee. The primary responsibilities of the DSMB are to: periodically review and evaluate the accumulated study data for participant safety; make recommendations to the Steering Committee based on these reviews regarding the continuation, modification or termination of the trial; and comment on the relevance of new external published data from other trials that may impact on patient safety or efficacy of the study treatments. The DSMB will meet and review 25(OH)D and safety data after 15, 30 and 52 participants have reached Day 7 of study enrolment. Alternatively, reviews will be conducted at least yearly. Specifically, the DSMB will review the percentage of participants meeting target 25(OH)D, those exceeding 200 and 250 nmol/L, and the occurrence of vitamin D related adverse events (hypercalciuria, hypercalcemia), and serious adverse events potentially related to study drug. With the exception of the 25(OH)D results, the DSMB will initially be blinded to study group allocation for safety data and any clinical or biochemical outcome data requested. However, the DSMB will also be provided with the group identity codes under separate cover so that they can evaluate the data with knowledge of treatment group if desired. If safety concerns arise, more frequent meetings will be initiated, and the trial may be terminated. The DSMB Chair can also request a full meeting at any time. The DSMB Chair will receive immediate notification and reports of serious adverse events determined to be related to the study drug. In addition, the DSMB Chair will receive a report for all deaths and all requirements for renal replacement therapy, regardless of whether they are thought to be related to the VITdAL-PICU study.

Adaptive design and stopping rules

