To ensure that we are not enrolling patients unnecessarily, it was decided at the Sept 8, 2015 Steering committee meeting that the DSMB also review the 25(OH)D primary outcome data after 30 and 52 patients have completed all study procedures (primary outcome data will not be reviewed after 15 patients). The following criteria will be used to determine whether the trial should be stopped early for the primary outcome.

- Proportion achieving 25(OH)D \geq 75 nmol/L
 - After 30 participants: Point estimate of \geq 90% (lower confidence interval would be approximately 75%)

- After 52 participants: Point estimate of >75% (lower confidence interval would be approximately 60%)

*If the DSMB was to see a signal in the SAE or vitamin D related adverse event data and felt that enrolling another 15 participants would help resolve whether the difference could be real they could recommend against stopping.

- Participants achieving potentially toxic levels
 - If more than 10% of study participants achieved 25(OH)D above 250 nmol/L, even in the absence of clinical sequelae, we will consider modifying the loading dose downward (these cases would be reviewed for signs of biochemical or clinical toxicity by the DSMB).

COST-EFFECTIVENESS SUB-STUDY

As part of the full phase III VITdAL-PICU trial we do intend to perform a cost effectiveness sub-study. A recently funded and active research project (DEMAND-PICU Study) by one of our co-applicants, [name], seeks to determine the costs associated with critical illness. These costs have not been previously documented in Canada, and will include those related to hospital (base rate, nursing ratios, etc.), patient (ECMO, dialysis, surgery, imaging, etc.) and family factors (distance from home, travel, hotel expenses). We anticipate the results of this study to be available well prior to the phase III trial. If funding for our pilot is secured and additional information is required, we will collect data as part of the VITdAL-PICU.

During the current phase II study, resource utilization data collected as part of the REB approved DEMAND-PICU study (REB no. 14/211X and 14/191X) will be linked to patients enrolled in VITdAL-PICU at CHEO to perform a pilot cost effectiveness sub-study. Data collection for the DEMAND-PICU study will run until February 2016, after which time we will continue to collect the same resource utilization data for VITdAL-PICU patients (if funding permits).

PARTICIPATING CENTRES

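### The interim stopping rule on 25(OH)D has no scheduled assay to feed it, and two sections give different triggers for the same looks

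*Combined protocol and SAP*

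**What the plan says.** All references are to the combined protocol and SAP.

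- **Assay timing.** Blood and Urine Sampling: "Blood samples at each time point will be analyzed for 25(OH)D levels at study close out". Appendix I, which covers sub-sites only, has the screening and discharge samples assayed in real time. The Day 1, 2, 3 and 7 samples are stored and sent to the coordinating centre, with shipping frequency left to recruitment rate and site preference.
- **What the DSMB receives.** Role of the Data Safety Monitoring Board: "the DSMB will review the percentage of participants meeting target 25(OH)D, those exceeding 200 and 250 nmol/L". The same section shows that unblinded levels are expected at the looks: "With the exception of the 25(OH)D results, the DSMB will initially be blinded to study group allocation".
- **The rule.** Adaptive Design and Stopping Rules allows an early stop if at least 90% are at or above 75 nmol/L after 30 participants, or more than 75% after 52. The stated aim is to avoid unnecessary enrolment.
- **The trigger.** The DSMB section says: "The DSMB will meet and review 25(OH)D and safety data after 15, 30 and 52 participants have reached Day 7 of study enrolment". The stopping-rules section says: "the DSMB also review the 25(OH)D primary outcome data after 30 and 52 patients have completed all study procedures".
- **The outcome itself.** Study Endpoints uses the Day 7 level, with a 48-hour window either side, and falls back on Day 3 if Day 7 is missing. Measurement of Outcomes at Follow-Up names liquid chromatography-mass spectrometry for final reporting.

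**The concern.** A stopping rule can be applied only if its input exists when the board meets. Laboratory and site staff who follow the sampling section literally would hold the Day 7 samples until the trial ends. The board would then meet with whatever discharge values happened to be available, possibly from a different assay from the one used for the final result.

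The trigger conflict matters for the same purpose. At the second look the plan assumes there are still patients left to save, since the DSMB may decide that "enrolling another 15 participants would help resolve whether the difference could be real". If the look waits for Day 90 while enrolment goes on, many or all of those 15 may already have been enrolled. The stake is the usefulness of the second look. The final estimate does not depend on it.

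**Working it through.** **1. Assay timing, section against section**

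- The rule needs a Day 7 value, or its Day 3 substitute, for each child counted.
- The sampling section assays every time point at close-out. For the coordinating centre, this general sentence is the only statement on when Day 3 and Day 7 samples are assayed.
- For sub-sites, Appendix I stores those samples, gives no assay date and ties no shipment to a DSMB look.
- The remaining source is the discharge sample. Study Duration and Appendix G describe it as the last test or sample before discharge. Research blood is drawn only through existing lines or with clinical bloodwork, so the Day 7 sample may itself be the last one. The documents give no distribution of discharge day, so the fraction of children covered cannot be calculated.
- Appendix G assays the discharge sample on the rapid device or at a certified laboratory. Final reporting uses mass spectrometry.

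The 75 nmol/L rule therefore has no scheduled input.

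**2. Does the rule have a real chance of acting?**

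Assume 2:1 allocation gives 20 and 35 treated children at the two looks. Stopping then needs at least 18 of 20, or at least 27 of 35. Summing the exact binomial probabilities over both looks, the chance of stopping by the second look is about 48% if the true proportion is 75%, and about 91% if it is 84%. (The sample-size section derives 16% below target before lowering its expectation to 75% at target.)

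**3. Size of the trigger conflict**

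The plan's own figure first: 67 − 52 = 15 places left at the second look, as the stopping-rules section says. At the first look, 67 − 30 = 37.

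Accrual rates from Feasibility of Recruitment:
- 67 patients over the 2 years allowed: 67/24 = 2.79 per month.
- The stated figure for the coordinating centre: about 5 per month.
- 67 patients from one year's admissions: 67/12 = 5.58 per month.

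None is an upper bound, because the same section expects other sites to add to the rate.

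Assume enrolment continues while a look is pending (the documents are silent), and that a month is 30.44 days. Then:

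places left = places at trigger count − rate × lag/30.44, with a minimum of 0.

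| | 2.79/month | 5/month | 5.58/month |
|---|---|---|---|
| Enrolled in 9 days (Day 7 + 48 h) | 0.83 | 1.48 | 1.65 |
| Left of 15 | 14.2 | 13.5 | 13.4 |
| Enrolled in 90 days | 8.25 | 14.78 | 16.51 |
| Left of 15 | 6.7 | 0.2 | 0 |
| Left of 37, first look, 90 days | 28.7 | 22.2 | 20.5 |

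The Poisson probability that at least 15 children are enrolled in 90 days is 2%, 51% and 68%. The rate at which the expected number left reaches zero is 15 × 30.44/90 = 5.07 per month.

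Shipping and assay take time too. With an assumed 14 to 28 days added to the 9 (lag 23 to 37 days), the Day 7 trigger leaves 12.9 to 11.6, 11.2 to 8.9, or 10.8 to 8.2 of the 15.

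**4. What the earlier trigger gives up**

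Children at Day 90 when the look falls on Day 9 of the 52nd child = 52 − rate × 81/30.44 = 44.6, 38.7 or 37.1 (86%, 74% or 71%). So 14% to 29% would not yet have full safety follow-up.

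**The case against.** **Intent is clear.** The DSMB sections and Frequency of Analyses all presuppose interim levels, so what is missing may be only logistics. The DSMB terms of reference or the laboratory SOP, neither of which is available here, may supply it. This stands as to intent. It does not remove the explicit close-out sentence, and intent does not settle the samples, the assay or the dates.

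**Real-time discharge values exist, and shipping during the trial is contemplated.** Both are true. A reader might infer that the rule lacks its input for most children. The documents do not support that: the last sample before discharge can be the Day 7 sample, and nothing shows how often. Appendix I also does not govern the coordinating centre. Nor should the task order in the Appendix K timeline be read as a schedule placing the assays after the interim analysis.

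**The trigger harm rests on stacked assumptions.** Loss of Follow-Up ends follow-up at 90 days, discharge or death, so completion may come well before Day 90. Enrolment might pause during a look; two 90-day waits would then cost 2 × 90/30.44 = 5.9 months, against 0.6 months for two 9-day waits. At 2.79 per month even the Day 90 reading leaves 6.7 places. All this stands, and the figures are therefore conditional. The later trigger also has merit: Study Duration calls three months adequate to screen for side effects.

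**Other apparent inconsistencies.** A reader might count the aggregate SAE review, tied to the initial loading dose, as a third trigger. A reader might also see a conflict over what is reviewed at 15 patients. The first is a different review, and the second has a coherent reading (safety levels only). Neither is a defect in the 75 nmol/L rule.

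**Conclusion.** The point holds as an internal conflict that should be fixed before the first look that applies the rule. Followed literally, the close-out schedule leaves the 75 nmol/L stopping rule with no scheduled Day 7 or Day 3 input, and the same two looks carry two triggers. The documents do not show that the looks could not be held.

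The assay limb rests on the text alone. The size of the trigger limb depends on three things: completion meaning Day 90, enrolment continuing during the look, and the accrual rate. At about 5 per month or more the later trigger leaves the second look almost nothing to save; at 2.79 per month it roughly halves what is left. The first look remains useful in every scenario.

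The worst outcome is enrolment up to the planned maximum of 67. The final primary estimate and the real-time calcium checks are unaffected.

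**What to change.** **(a) Assay.** Amend Blood and Urine Sampling and Appendix I so that Day 7 samples, or Day 3 where Day 7 is missing, from all sites including the coordinating centre are batch-assayed before the 30- and 52-patient looks, with the rest at close-out. Name the assay and say whether the interim value feeds the final estimate. Allow a re-run only if plasma volume permits: samples are 1.5 mL in the smallest children and also serve several other assays. Keep interim results from blinded study staff. The blinding section includes the statisticians, and with 0% of controls expected at target, levels can reveal allocation.

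**(b) Trigger.** Use one trigger in both DSMB sections for the 75 nmol/L rule, and say whether enrolment continues while a look is pending. Day 7 with its +48-hour window fits the stated aim of not enrolling unnecessarily. If the later trigger is kept, give the reason.

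**Cost.** A short amendment.
- Shipments: three sub-sites (Participating Centres) × two looks = 6 interim shipments, or 2 × 2 = 4 if only the two in the Study Summary take part. Some may coincide with shipments already planned.
- Assays: up to 30 done early for the first look and 52 in total by the second. If 5% of Day 7 samples are missing, 30 × 0.05 = 1.5 and 52 × 0.05 = 2.6 of these would be Day 3 substitutes.
- Some between-batch variation, which repeated controls can check.
- The shorter safety follow-up at the second look calculated above, which the DSMB can weigh under its existing option to recommend against stopping.

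No additional patients or blood draws are needed.
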